7.3 Follow-up Study Visit 2, Week 4, Day 28 (Allowable Days 21-35)

The following procedures and assessments will be performed at Visit 2, Week 4, Day 28:

1. Participants will return on Day 28. Staff will review the memory aid with the participant. The participant will be asked about symptoms, concomitant medications and any medical problems since the last visit, which will be recorded on the appropriate CRF. The participant will be asked to provide exact dates and times of the study product administration.
2. Medical, gynecological and sexual history to include assessment of STI and HIV risk
3. Symptom-directed physical and pelvic examination by a study physician or nurse that will include vital signs, including temperature, and examination of respiratory and cardiovascular systems, as well as assessment of symptoms and adverse events
4. The pelvic examination will be conducted in the following order:
 - a. Examination of the external genitalia
 - b. Speculum insertion and examination of vagina, fornices and cervix with naked eye. Water will be used to ease speculum insertion. No lubricant should be used as it could contain chlorhexidine which may kill *Lactobacillus*.
 - c. Vaginal pH
 - d. Vaginal swab for wet mount taken from the posterior fornix for yeast vaginitis and clue cells and for amine test (whiff test)
 - e. Vaginal swab for Gram stain (Nugent scoring system)
 - f. Vaginal swabs (no more than two) for storage and future identification of vaginal bacteria, and possible multiomic (e.g. proteomics, metabolomics, etc.) testing
 - g. Vaginal swabs for *L. crispatus* identification with qPCR
 - h. If indicated, cervical (or vaginal) swab for nucleic acid amplification of *N. gonorrhoeae*, *C. trachomatis*, and *T. vaginalis*
5. If indicated, clean catch urine dipstick; urinalysis if abnormal results indicate
6. If indicated, urine β hCG pregnancy test
7. All clinical and laboratory findings at the time of the evaluation will be recorded on the CRF. These findings will include observations present on the pelvic exam such as genital findings including location; presence or absence, and character of vaginal or cervical discharge or lesions; and results of any on-site tests.
8. Participants will be reminded not to use scented tampons or any other vaginal products through Visit 7 (Week 24, Day 168).
9. Participants will be reminded to abstain from sexual intercourse for 12 hours after each study product application and for 12 hours before the remaining study visits at Visit 3 (Week 8, Day 56), Visit 4 (Week 12, Day 84) and Visit 7 (Week 24, Day 168).
10. Participants will receive non-spermicidal lubricated condoms for their male sexual partners. Participants will be encouraged to use condoms if they engage in vaginal intercourse through Visit 7 (Week 24, Day 168).
11. Participants will be asked if they still have the remaining applicators for the twice weekly doses stored at home. If not, they will receive additional pre-filled applicators to administer twice weekly through week 11. Participants will be instructed to transport the pre-filled applicators while avoiding exposure to high temperatures.

12. Participants will be instructed to collect all used applicators and store them as described in the MOP and to return all used applicators at their next visit, Visit 3 (Week 8, Day 56).
13. Applicators used since the last study visit will be collected. Applicators will be stained and tested as described in the MOP.
14. An appointment for the follow-up visit will be scheduled. Depending on the time of the enrollment and the average length of the participant's menstrual cycle, careful attention should be paid to the approximate time of the participant's next menstrual period when scheduling those visits. Later adjustments of those dates may be necessary.

Women with vaginal discharge or vaginitis symptoms who were diagnosed with yeast on the wet mount during the follow-up visit will be referred for standard treatment and continue to receive study product.

If the test results at the follow-up visit suggest a urinary tract infection, cervicitis or vulvovaginitis, the participant will be referred for standard treatment and continue to receive study product.

If the clinician suspects the woman to have developed an STI since the last visit, appropriate tests will be conducted and if needed the woman will be referred to standard of care treatment in compliance with current CDC STD Treatment Guidelines. The participant should be treated in case of positive findings and continue to use study product.

Women who develop *symptomatic* BV confirmed by wet mount Amsel criteria ≥ 3 (with or without confirmatory Gram stain) at least 4 weeks after the last MetroGel treatment will be retreated with MetroGel. This practice follows CDC treatment guidelines and FDA recommendations. The 5-day course of MetroGel will begin as soon as possible. Women will skip their regularly scheduled dose of study product until 24 hours after their last dose of MetroGel when study product dosing will continue twice weekly. Women diagnosed with *asymptomatic* BV during the follow-up visit will not be retreated with MetroGel.

7.4 Follow-up Study Visit 3, Week 8, Day 56 (Allowable Days 49-63)

The same procedures and assessments performed at Study Visit 2, Week 4, Day 28 will also be done at this visit.

7.5 Follow-Up Study Visit 4, Week 12, Day 84 (Allowable Days 77-91)

The following procedures and assessments will be performed at Visit 4, Week 12, Day 84:

1. Participants will return on Day 84. Staff will review the memory aid with the participant. The participant will be asked about symptoms, concomitant medications and any medical problems since the last visit, which will be recorded on the appropriate CRF. The participant will be asked to provide exact dates and times of the study product administration.
2. Medical, gynecological and sexual history to include assessment of STI and HIV risk

3. Symptom-directed physical and pelvic examination by a study physician or nurse that will include vital signs, including temperature, and examination of respiratory and cardiovascular systems, as well as assessment of symptoms and adverse events
4. The pelvic examination will be conducted in the following order:
 - a. Examination of the external genitalia
 - b. Speculum insertion and examination of vagina, fornices and cervix with naked eye. Water will be used to ease speculum insertion. No lubricant should be used as it could contain chlorhexidine which may kill *Lactobacillus*.
 - c. Vaginal pH
 - d. Vaginal swab for wet mount taken from the posterior fornix for yeast vaginitis and clue cells and for amine test (whiff test)
 - e. Vaginal swab for Gram stain (Nugent scoring system)
 - f. Vaginal swabs (no more than two) for storage and future identification of vaginal bacteria, and possible multiomic (e.g. proteomics, metabolomics, etc.) testing
 - g. Vaginal swabs for *L. crispatus* identification with qPCR
 - h. If indicated, cervical (or vaginal) swab for nucleic acid amplification of *N. gonorrhoeae*, *C. trachomatis*, and *T. vaginalis*
5. If indicated, clean catch urine dipstick; urinalysis if abnormal results indicate
6. If indicated, urine β hCG pregnancy test
7. All clinical and laboratory findings at the time of the evaluation will be recorded on the CRF. These findings will include observations present on the pelvic exam such as genital findings including location; presence or absence, and character of vaginal or cervical discharge or lesions; and results of any on-site tests.
8. Participants will be asked to answer a detailed self-administered questionnaire assessing the acceptability of the study product and the applicator to evaluate the possible change of attitudes over time.
9. Participants will be reminded not to use scented tampons or any other vaginal products through Visit 7 (Week 24, Day 168).
10. Participants will be reminded to abstain from sexual intercourse for 12 hours before study Visit 7 (Week 24, Day 168).
11. Participants will receive non-spermicidal lubricated condoms for their male sexual partners. Participants will be encouraged to use condoms if they engage in vaginal intercourse through Visit 7 (Week 24, Day 168).
12. Applicators used since the last study visit will be collected. Applicators will be stained and tested as described in the MOP.
13. An appointment for a telephone interview at Visit 5 (Week 16, Day 112) and at Visit 6 (Week 20, Day 140) will be scheduled.
14. An appointment for the next follow-up visit, Visit 7 (Week 24, Day 168) will be scheduled. Depending on the time of the enrollment and the average length of the participant's menstrual cycle, careful attention should be paid to the approximate time of the participant's next menstrual period when scheduling those visits. Later adjustments of those dates may be necessary.

Women with vaginal discharge or vaginitis symptoms who were diagnosed with yeast on the wet mount during the follow-up visit will be referred for standard treatment.

If the test results at the follow-up visit suggest a urinary tract infection, cervicitis or vulvovaginitis, the participant will be referred for standard treatment.

If the clinician suspects the woman to have developed an STI since the last visit, appropriate tests will be conducted and if needed the woman will be referred to standard of care treatment in compliance with current CDC STD Treatment Guidelines. The participant should be treated in case of positive findings.

Women who develop symptomatic BV confirmed by wet mount Amsel criteria ≥ 3 (with or without confirmatory Gram stain) at least 4 weeks after the last MetroGel treatment will be retreated with MetroGel. This practice follows CDC treatment guidelines and FDA recommendations. The 5-day course of MetroGel will begin as soon as possible. Women will skip their regularly scheduled dose of study product until 24 hours after their last dose of MetroGel when study product dosing will continue twice weekly. Women diagnosed with asymptomatic BV during the follow-up visit will not be retreated with MetroGel.

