6.1.2 Formulation, Packaging, and Labeling

LACTIN-V and placebo

Each applicator will contain a LACTIN-V powder formulation containing *L. crispatus* CTV-05 at a potency of 2×10^9 cfu/dose. [REDACTED]

. A

matching placebo formulation without *L. crispatus* CTV-05 is supplied in an identical applicator containing placebo powder.

LACTIN-V or placebo pre-filled applicators will be individually packaged in heat-sealed foil pouches, each containing one desiccant packet. Each participant will receive one box containing 25 applicators. Each foil pouch and box will be labeled with the study number and unique participant number.

The foil pouches and boxes will be labeled by the Osel Study Product Supplier. Each label will contain the study number and the FDA-required cautionary statement "*Caution- New drug -Limited by Federal Law to Investigational Use.*" The label of each box of study product applicators will also include the unique participant number and the statements: "*Store at home in a cool, dry place out of reach of children (at room temperature).*"

MetroGel vaginal gel

MetroGel vaginal gel is a gelled purified water solution, containing metronidazole at a concentration of 7.5 mg/g (0.75%). The gel is formulated at pH 4.0. The gel also contains carbomer 934P, edetate disodium, methylparaben, propylparaben, propylene glycol and sodium hydroxide.

MetroGel vaginal gel is supplied in a 70 gram tube. Each participant will receive one box of MetroGel vaginal gel sufficient for the 5-day course of treatment.

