6.2 Dosage, Preparation, and Administration of Study Product

LACTIN-V and placebo

Eligible participants will be instructed on how to insert the pre-filled applicator (LACTIN-V at 2×10^9 cfu/dose, or the placebo control substance) and will administer the first dose under direct supervision by the study clinician before leaving the clinic (Day 1). Study personnel will verify that each carton contains all 24 remaining applicators and this will be recorded on the appropriate Case Report Form (CRF). Participants will be instructed to administer one dose once a day at bedtime for the next 4 days (beginning on Day 2), and then two times a week for 10 weeks. The remaining 20 applicators will be used for the two doses each week during weeks 2 through 11.

MetroGel vaginal gel

Participants will be instructed to administer one dose once a day at bedtime for 5 days initiated as soon as possible (ideally within 5 days of diagnosis at the screening or follow-up visit for symptomatic participants, or within 24 days of the screening visit for asymptomatic participants (see section 7.0 for additional details).

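### Protocol 7.5 and 7.8 repeat the Visit 2 instruction to resume study product after MetroGel re-treatment, although scheduled dosing ends in Week 11

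*Protocol*

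**What the plan says.** Protocol 6.1.2 sets the supply: "Each participant will receive one box containing 25 applicators". Protocol 6.2 sets the schedule: one dose in clinic on Day 1, four daily doses, then two a week. It adds: "The remaining 20 applicators will be used for the two doses each week during weeks 2 through 11". Resupply at Visit 2 (7.3 item 11) and at unscheduled visits (7.10 item 10) is limited to Week 11. Visit 3 follows Visit 2 by cross-reference: "The same procedures and assessments performed at Study Visit 2, Week 4, Day 28 will also be done at this visit". Appendix A provides for dispensing product, if indicated, at Visits 2 and 3, but not at Visit 4.

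For symptomatic BV at a follow-up visit, 7.3 prescribes five days of MetroGel. Study product is paused until 24 hours after the last MetroGel dose, "when study product dosing will continue twice weekly". The same sentence stands in 7.5 (Visit 4), 7.8 (Visit 7) and 7.10 (unscheduled visits), with no end date.

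Secondary objectives 3 and 4 (Protocol 3.1.2) describe the Week 24 assessment as falling twelve weeks after the last dose.

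**The concern.** The rest of 7.5 was edited for the end of dosing. For urinary infection, cervicitis or vulvovaginitis, 7.3 reads "the participant will be referred for standard treatment and continue to receive study product", while 7.5 stops at "cervicitis or vulvovaginitis, the participant will be referred for standard treatment". The yeast and STI paragraphs make the same cut. At Visit 2 women are reminded to "abstain from sexual intercourse for 12 hours after each study product application". At Visit 4 that part of the reminder is gone, and so is the resupply step. Only the BV paragraph kept its Visit 2 form, so it reads as a carry-over rather than a decision to extend dosing.

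A site could still take it as live. It says affirmatively that dosing continues, and Appendix A marks the study-intervention row at Visit 4. Item 12 of 7.5 collects used applicators and does not mention unused ones, whereas 7.9 collects both. A woman who skipped doses during an earlier re-treatment, or missed some, could reach Visit 4 with product in hand.

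What is at stake is the off-product interval before Visit 7. Late LACTIN-V dosing could affect that woman's Visit 7 CTV-05 colonization (secondary objective 3, SAP Table 22) and her by-visit Day 168 recurrence, which SAP 8.2 tests by chi-square.

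**Working it through.** **Inputs.** Dosing schedule from Protocol 6.2 and box size from 6.1.2. Visit windows from the section titles: Visit 2 Days 21–35, Visit 3 Days 49–63, Visit 4 Days 77–91, Visit 7 Days 161–175. The five-day MetroGel course and 24-hour wait come from 7.3 and 7.5.

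**The plan's own figure.** Doses = 1 + 4 + 2 × 10 = 25, which equals one box. Dosing weeks = 1 + 10 = 11. The protocol maps Week 12 to Day 84, so Week k ends on Day 7k and Week 11 ends on Day 77. The stated count and end of dosing are reproduced. With full dosing no applicator is left.

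**Earliest restart.** If MetroGel starts on the evening of visit day v, it runs from v to v + 4, and product resumes on v + 5.

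| Visit | Visit day v | Restart v + 5 | Relative to Day 77 |
|---|---|---|---|
| 2 | 21 to 35 | 26 to 40 | inside dosing period |
| 3 | 49 to 63 | 54 to 68 | inside dosing period |
| 4, earliest | 77 | 82 | 5 days after |
| 4, target | 84 | 89 | 12 days after |
| 4, latest | 91 | 96 | 19 days after |

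The sentence works at Visits 2 and 3. At Visit 4 no restart falls within scheduled dosing. A later MetroGel start moves the restart later still.

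**Off-product time at Visit 7, taking Day 77 as the planned last dose.**
- Planned: 161 − 77 = 84 days, 168 − 77 = 91 days, 175 − 77 = 98 days (12.0, 13.0 and 14.0 weeks).
- One restarted dose, Visit 4 on Day 84 and Visit 7 on Day 168: 168 − 89 = 79 days (11.3 weeks), a cut of 91 − 79 = 12 days.
- Over the Visit 4 window the cut is 5 to 19 days, whatever the Visit 7 date.
- Over both windows the remaining gap runs from 161 − 96 = 65 days (9.3 weeks) to 175 − 82 = 93 days (13.3 weeks).
- Each further leftover dose removes about 7 / 2 = 3.5 days more.

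**If dosing could run to Day 84.** A restart is then in time when v + 5 ≤ 84, that is, for visits on Days 77–79. For a Day 84 visit the cut falls to 89 − 84 = 5 days, and for a Day 91 visit to 96 − 84 = 12 days.

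**The case against.** The strongest reply is that the sentence has little force at Visit 4. It speaks of skipping a scheduled dose and continuing, and after Week 11 there is none to skip or continue. Nothing is dispensed at Visit 4. SAP 4.4.3 says that remaining doses should not be used up and that unused ones come back. SAP Table 56 and Listing 7 record unused applicators returned, and the manual of procedures, which is not among the documents, may cover collection. Much of this stands. Harm needs symptomatic BV at Visit 4, leftover applicators, and a site that follows 7.5 rather than SAP 4.4.3. But the SAP rule was written for missed doses and sits in the analysis plan, while the visit text that sites work from says the opposite.

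A reader might infer that the sentence can have no valid use after Visit 4 because Day 77 is a hard stop. The documents do not go that far. SAP 4.4.3 refers to women who cannot make up all missed doses after Week 11, which can be read as allowing some make-up dosing then. The wording of the Week 24 objectives and the Appendix A mark at Visit 4 loosely suggest dosing to Week 12. On that reading the cut is smaller. None of these places sets a twice-weekly schedule beyond Week 11, so the conflict remains.

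The size is also modest against the plan's own tolerance. The twelve weeks in the objectives is nominal, since the planned gap is 84 to 98 days. In the central case 79 days is 5 short of 84, which is less than the seven-day margin on Visit 7.

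**Conclusion.** This is a minor internal inconsistency in a site instruction. Protocol 7.5 and 7.8 keep a restart rule that conflicts with the end of dosing in 6.2. At 7.8 no outcome visit follows, so it has no practical effect. At 7.5 one restarted dose shortens off-product time by 12 days in the central case (91 to 79), and by 5 to 19 days over the Visit 4 window. This assumes a last planned dose on Day 77 and MetroGel started on the visit day. The cut is smaller if make-up dosing after Week 11 is allowed. The number of women is not given and is probably small.

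A reader might infer that the efficacy results are compromised or that the SAP has a gap. The documents do not support that. Any restart follows the Visit 4 assessment, so the primary endpoint is unaffected. Cumulative Week 24 recurrence is essentially unaffected, because SAP 6.3.2 counts women who begin other BV treatment as recurrent, and the Table 20 sensitivity analysis removes women given additional BV treatment. Slight contamination of Visit 7 colonization and by-visit Day 168 recurrence remains possible. The days-since-last-dose displays (Tables 39–42, Figures 6–9) and the blinded case review (SAP 6.3.2.5) would help expose or handle it.

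**What to change.** Issue a protocol clarification letter with three changes:

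- Delete the skip-and-continue sentence from 7.5 and 7.8.
- In the BV paragraph of 7.10, limit the sentence to visits during the dosing period, through Week 11. Unscheduled visits can fall later (7.6 invites them between Visits 4 and 7), and item 10 limits only the resupply.
- Have 7.5 item 12 also collect unused applicators, in line with 7.9 and SAP 4.4.3.

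Section 7.3 needs no edit, because item 11 already stops at Week 11 and restarts after Visits 2 and 3 fall inside the dosing period. No SAP change is needed. The letter is the only cost.

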7.6 Telephone Interview, Visit 5, Week 16, Day 112 (Allowable Days 105-119)

Between Visit 4 (Week 12, Day 84) and Visit 7 (Week 24, Day 168), communication with participants will be continued by monthly telephone interviews.

1. Participants will be called for a prearranged telephone interview at Day 112. Staff will review the memory aid with the participant. The participant will be asked about symptoms, concomitant medications, last menses, sexual activity and any medical problems since the last visit, which will be recorded on the appropriate CRF.
2. Participants are invited to present at the clinic for an unscheduled visit if the site investigator deems it necessary after reviewing any medical problems or symptoms.
3. Participants will be reminded not to use scented tampons or any other vaginal products through Visit 7 (Week 24, Day 168).
4. Participants will be reminded to abstain from sexual intercourse for 12 hours before the last study visit, Visit 7 (Week 24, Day 168).
5. An appointment for the next telephone interview at Visit 6 (Week 20, Day 140) will be confirmed or rescheduled if necessary.
6. An appointment for the final visit, Visit 7 (Week 24, Day 168) will be confirmed. Depending on the time of the enrollment and the average length of the participant's menstrual cycle, careful attention should be paid to the approximate time of the participant's next menstrual period when scheduling those visits. Later adjustments of those dates may be necessary.

If the participant fails to cancel the appointment and reschedule, and is unreachable during the agreed upon time for the telephone interview, the study team will make three attempts to reach the participant to reschedule the telephone interview.

7.7 Telephone Interview, Visit 6, Week 20, Day 140 (Allowable Days 133-146)

The same assessments and instructions at Telephone Interview, Visit 5, Week 16, Day 112 will also be done during this telephone interview.

7.8 Final Study Visit 7, Week 24, Day 168 (Allowable Days 161-175)

The following procedures and assessments will be performed at Visit 7, Week 24, Day 168.

1. Participants will return on Day 168. Staff will review the memory aid with the participant. The participant will be asked about symptoms, concomitant medications and any medical problems since the last visit, which will be recorded on the appropriate CRF.
2. Medical, gynecological and sexual history to include assessment of STI and HIV risk
3. Symptom-directed physical and pelvic examination by a study physician or nurse that will include vital signs, including temperature, and examination of respiratory and cardiovascular systems, as well as assessment of symptoms and adverse events
4. The pelvic examination will be conducted in the following order:
 - a. Examination of the external genitalia
 - b. Speculum insertion and examination of vagina, fornices and cervix with naked eye. Water will be used to ease speculum insertion. No lubricant should be used as it could contain chlorhexidine which may kill *Lactobacillus*.
 - c. Vaginal pH
 - d. Vaginal swab for wet mount taken from the posterior fornix for yeast vaginitis and clue cells and for amine test (whiff test)
 - e. Vaginal swab for Gram stain (Nugent scoring system)
 - f. Vaginal swabs (no more than two) for storage and future identification of vaginal bacteria, and possible multiomic (e.g. proteomics, metabolomics, etc.) testing
 - g. Vaginal swabs for *L. crispatus* identification with qPCR
 - h. If indicated, cervical (or vaginal) swab for nucleic acid amplification of *N. gonorrhoeae*, *C. trachomatis*, and *T. vaginalis*
5. If indicated, clean catch urine dipstick; urinalysis if abnormal results indicate urinalysis
6. If indicated, urine β hCG pregnancy test.
7. All clinical and laboratory findings at the time of the evaluation will be recorded on the CRF. These findings will include observations present on the pelvic exam such as genital findings including location; presence or absence, and character of vaginal or cervical discharge or lesions; and results of any on-site tests.

Women with vaginal discharge or vaginitis symptoms who were diagnosed with yeast on the wet mount during the follow-up visit will be referred for standard treatment.

If the test results at the follow-up visit suggest a urinary tract infection, cervicitis or vulvovaginitis, the participant will be referred for standard treatment.

If the clinician suspects the woman to have developed an STI since the last visit, appropriate tests will be conducted and if needed the woman will be referred to standard of care treatment in compliance with current CDC STD Treatment Guidelines. The participant should be treated in case of positive findings.

Women who develop *symptomatic* BV confirmed by wet mount Amsel criteria ≥ 3 (with or without confirmatory Gram stain) at least 4 weeks after the last MetroGel treatment will be retreated with MetroGel. This practice follows CDC treatment guidelines and FDA recommendations. The 5-day course of MetroGel will begin as soon as possible. Women will skip their regularly scheduled dose of study product until 24 hours after their last dose of MetroGel when study product dosing will continue twice weekly. Women diagnosed with *asymptomatic* BV during the follow-up visit will not be retreated with MetroGel.

